We anticipate that 30-60 participants will not have a baseline specimen that can be used to determine nAb status. The primary analysis in the nAb-negative subgroup will be restricted to participants with known (nAb-negative) status, while the total cohort will include both, participants with known and unknown antibody status. As a sensitivity analysis, we will impute nAb status for these participants using baseline characteristics that include age, oxygen requirements, duration of time between symptom onset and randomization, and SARS-CoV-2 vaccination status. Using a logistic regression model, baseline predictors of nAb status will be determined. The coefficients from the regression model will be used to classify the participants with missing nAb status as negative or positive. For the imputed as nAb-negative if the predicted probability of having been nAb-negative at baseline is 50% or greater, 60% or greater, and 70% or greater. The primary comparison for the sustained recovery endpoint in the nAb-negative subgroup will be repeated including both those with known nAb-negative status as well as those who were imputed as nAb-negative, in separate analyses for each of the three imputation cut-points.

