For the AZD7442 investigational agent, additional subgroup analyses will be carried out for the following subgroups defined at baseline; subgroups, hypotheses and analyses are described in Appendix E:

- SARS-CoV-2 vaccination status. Subgroups will be formed by vaccination status and by type of vaccine.
- Immunosuppressive state
- SARS-CoV-2 viral genome sequence and variant lineage.

As a **general rule**, subgroup analyses will be carried out using statistical models that are stratified by disease severity; for time-to-event analyses, stratified Fine-Gray or Cox proportional hazards models will be used, while for other outcomes, models will include the disease severity indicator as covariate. Global tests for heterogeneity of the treatment effect across subgroups will be carried out, by adding the interaction between the subgroup indicator and the treatment group indicator to a model that contains the treatment group indicator and subgroup variable as "main effects". In case the subgroup was formed by categorizing a continuous variable, the models used for the subgroup analyses will contain the (continuous) subgroup variable as covariate, and the interaction term in the expanded model will be formed between the subgroup indicator and the continuous variable.

Subgroup analyses for the primary endpoint of **time to sustained recovery** will use the Fine-Gray model (with death as competing risk), stratified by disease severity at study entry. Within each subgroup, the number and percent of recovered participants and median time to recovery will be calculated by treatment group, and sHRs with 95% CIs comparing the investigational agent versus control will be estimated. Global tests for heterogeneity of the treatment effect across subgroups will be carried out, by adding the interaction between the subgroup indicator and the treatment group indicator to the model that contains data across all subgroups. Median time to recovery will be estimated using Aalen-Johansen estimators.

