The hypotheses in this subsection were developed for the comparison of AZD7442 (a longacting antibody combination) versus placebo, but apply more generally to monoclonal antibodies and antiviral agents. The outcomes, and the specific statistical models used for the subgroup analyses for each of the outcomes were described in Section 9.1.

The subgroup analyses by vaccination status and immunosuppression status address the following hypothesis:

Hypothesis 1: AZD7442 will have greater efficacy in non-vaccinated, compared to fully or partially vaccinated, study participants.

Hypothesis 2: AZD7442 will have greater efficacy in immunosuppressed, compared to not immunosuppressed, study participants.

For vaccination status, three mutually exclusive subgroups will be formed according to the current CDC definition of vaccination status:

- a. **Fully-vaccinated:** Subjects who have onset of acute symptoms of SARS-CoV-2 infection at least 14 days after receiving:
 - i. the **second** dose of a two-dose SARS-CoV-2 vaccine series, OR
 - ii. a **single** dose of the Janssen (J&J) SARS-CoV-2 vaccine
- b. Partially-vaccinated: Subjects who have:
 - i. received only one dose of two-dose SARS-CoV-2 vaccine series, OR
 - ii. onset of acute symptoms of SARS-CoV-2 infection prior to 14 day following the administration of the **second** dose of a two-dose SARS-CoV-2 vaccine series or a **single** dose of the Janssen (J&J) SARS-CoV-2 vaccine
- c. Non-vaccinated: Never received any dose of a SARS-CoV-2 vaccine.

Comment: Information about booster doses is not available.

Subgroup analyses by immunosuppressive status will consider three mutually exclusive subgroups, as defined below:

- **Immunosuppressed**, defined as any of the following:
 - Receiving antirejection medication (after solid or stem cell transplant)
 - Receiving biologic medicine to treat autoimmune disease or cancer, excluding IL-1 inhibitors, IL-6 inhibitors, Janus kinase inhibitors, and TNF inhibitors
 - HIV or other immunosuppressive condition
- Receiving any of the following immunomodulators: IL-1 inhibitors, IL-6 inhibitors, Janus kinase inhibitors, or TNF inhibitors, but not "immunosuppressed" as defined above
- None of the above

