Data from TICO and other studies have shown that baseline vaccination status and immunosuppressive status are correlated; in particular, in our study population of patients who are hospitalized with COVID-19 pneumonia, the proportion of immunosuppressed patients is higher among those who are fully *vaccinated* compared with those who are unvaccinated. In addition, studies have found that the decline over time in immunity varies between vaccines. In order to address potential confounding between vaccination status, immunosuppressive status, and type of vaccine, models for subgroup analyses by vaccination status will include immunosuppressive status and type of vaccine (mRNA versus other) as covariates. Similarly, models for subgroup analyses by immunosuppressive status will include vaccination status and type of vaccine as covariates.

The following **exploratory analyses** will be conducted if the sample size is large enough for meaningful analyses:

 Subgroups will also be formed by combinations of vaccination status and vaccine type (4 categories: not vaccinated; partially vaccinated; fully vaccinated with non-mRNA vaccine; fully vaccinated including at least one mRNA vaccine in the sequence). Models for this subgroup analysis will be adjusted for immunosuppressive status. • Subgroups will be formed by the bivariate combinations of *vaccination status and immunosuppressive status*.

In order to facilitate the interpretation of the results of the subgroup analyses, baseline levels of antibodies, antigen, and SARS-CoV-2 RNA will be summarized by vaccination status and by immunosuppressive status. These biomarkers include the following:

- SARS-CoV-2 antibody levels (nAb by GenScript, anti-N by BioRad, and anti-Spike IgG antibody levels by Quanterix assays)
- SARS-CoV-2 antigen levels in plasma
- Viral RNA by midturbinate swabs

See Appendix F for details on assays and outcome measures.

E-8 Subgroup Analyses by Viral Strain

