These cases were discussed on October 20, 2021, at a TICO investigator meeting and are also described in a memorandum from trial leadership to investigators in ACTIV-3 (TICO) on November 2, 2021. At that time we requested that investigators increase vigilance of participants who developed rash and simultaneously joint, muscle, and/or body aches.

On November 5, 2021, revised informed consents and drug information sheets that described these events were sent to sites and to the Advarra central IRB.

On December 7, 2021, all participants for whom rash adverse events had been reported through Day 28 were identified. Sites were asked to complete an eCRF for each event. Eleven participants experienced rash events through Day 28. The number and percentage of participants with a rash event by treatment group will be summarized. Rash events associated with myalgia, arthralgia, or generalized aches and pains will also be summarized by treatment group.

Line listing of events will include severity grade, rash characteristics, location, and other solicited events that occurred simultaneously.

No formal statistical testing will be carried out on the rash events alone. In a supplemental analysis for the Day 28 composite safety outcome which includes deaths, SAEs, organ failure, serious infection and grade 3 or 4 adverse events, the rash adverse events will be included as a separate component.

Subgroup Analyses

In addition to the subgroup analyses described in section 9, those described in section E-7 (vaccine and immunosuppressive status) and E-8 (viral strain) of Appendix E will be carried out for MP0420 for the outcomes listed in section 9.

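### The E-7 subgroup models, applied to MP0420, adjust for the other hypothesised effect modifier only as a covariate, which leaves the treatment-by-vaccination and treatment-by-immunosuppression interactions confounded with each other

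*SAP*

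**What the plan says.** SAP Appendix G states that "those described in section E-7 (vaccine and immunosuppressive status) and E-8 (viral strain) of Appendix E will be carried out for MP0420", without changing the models. E-7 sets out two hypotheses: "AZD7442 will have greater efficacy in non-vaccinated, compared to fully or partially vaccinated, study participants" and "AZD7442 will have greater efficacy in immunosuppressed, compared to not immunosuppressed, study participants". It then reports that, among patients hospitalised with COVID-19 pneumonia, immunosuppression is more frequent in the fully vaccinated than in the unvaccinated.

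The covariates have a declared purpose: "In order to address potential confounding between vaccination status, immunosuppressive status, and type of vaccine". For the vaccination subgroups, the models "will include immunosuppressive status and type of vaccine (mRNA versus other) as covariates". For the other factor: "Similarly, models for subgroup analyses by immunosuppressive status will include vaccination status and type of vaccine as covariates". E-7 names no treatment-by-covariate term.

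The general rule for heterogeneity tests, in section 9.1, is that they are done "by adding the interaction between the subgroup indicator and the treatment group indicator to a model that contains the treatment group indicator and subgroup variable", both entered as main effects. The only treatment interaction in the specified model is therefore the one with the subgroup factor under study.

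E-7 also plans exploratory subgroups that cross-classify vaccination and immunosuppression, and a four-level vaccination-and-type variable. Both depend on adequate numbers. The non-vaccinated are defined by "Never received any dose of a SARS-CoV-2 vaccine", and no value of vaccine type is given for them.

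**The concern.** Treatment is randomised, so immunosuppression cannot confound the treatment effect within a vaccination group. What it can confound is the difference in treatment effect between vaccination groups. If the agent works better in the immunosuppressed, and they are more common among the vaccinated, the vaccinated group shows a larger average effect even when vaccination itself changes nothing. Removing that requires a treatment-by-immunosuppression term. A main effect for immunosuppression only shifts the recovery rate equally in both arms.

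The model as naturally read therefore does not do what E-7 says the covariates are for. At stake is the reading of Hypotheses 1 and 2: a true vaccination difference could be hidden by the opposing pull of immunosuppression, and the reverse could happen in the immunosuppression model.

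**Working it through.** The plan gives no figure for the E-7 analyses, so there is none to reproduce. The check asks how much spurious interaction remains when the true treatment-by-vaccination interaction is zero.

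**Inputs from the documents:** 485 participants in the modified intention-to-treat cohort (Appendix G); 1:1 allocation (section 1.3); two-sided 0.05 level (section 3); both factors hypothesised as modifiers and positively correlated (E-7).

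**Assumed, because the documents are silent:** 30% vaccinated; immunosuppression in 20-40% of vaccinated and 10% of unvaccinated; recovery rate ratio (RRR) in the immunosuppressed 1.0, 1.5 or 2.0 times that in others; 85% recovered by Day 90; immunosuppression multiplies the recovery rate by 0.7. Both factors are treated as yes/no, although E-7 defines three levels of each.

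**Approximation:** log of spurious ratio = log(effect ratio by immunosuppression) × [P(IS | vaccinated) − P(IS | unvaccinated)].

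Example, 30% v 10% and effect ratio 1.5: 0.405 × 0.20 = 0.081, so the ratio is exp(0.081) = 1.084.

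**Simulation:** proportional sub-distribution hazards, deaths kept at risk to Day 90, n = 485, 1,000 runs per row. The ratio is RRR in vaccinated divided by RRR in unvaccinated; the true value is 1.

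| IS, vaccinated v unvaccinated | Effect ratio | Formula | No adjustment | Main effect (E-7) | Both interactions | False positives, E-7 / both | SE, E-7 / both |
|---|---|---|---|---|---|---|---|
| 30% v 10% | 1.0 | 1.000 | 1.008 | 1.006 | 1.006 | 4.9% / 5.1% | 0.220 / 0.227 |
| 20% v 10% | 1.5 | 1.041 | 1.043 | 1.041 | 1.000 | 4.8% / 4.2% | 0.218 / 0.220 |
| 20% v 10% | 2.0 | 1.072 | 1.079 | 1.078 | 1.008 | 6.8% / 5.8% | 0.217 / 0.219 |
| 30% v 10% | 1.5 | 1.084 | 1.085 | 1.080 | 0.996 | 6.8% / 5.7% | 0.218 / 0.225 |
| 30% v 10% | 2.0 | 1.149 | 1.146 | 1.146 | 0.999 | 9.1% / 5.2% | 0.217 / 0.225 |
| 40% v 10% | 1.5 | 1.129 | 1.140 | 1.135 | 1.013 | 10.2% / 5.4% | 0.219 / 0.234 |
| 40% v 10% | 2.0 | 1.231 | 1.246 | 1.246 | 1.012 | 18.3% / 4.2% | 0.218 / 0.233 |

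Monte Carlo error for a 5% rate is √(0.05 × 0.95 / 1000) = 0.7 percentage points.

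The main effect removes almost none of the bias, and the added interaction removes essentially all of it. At n = 20,000 (30% v 10%, ratio 2.0) the three models give 1.155, 1.154 and 1.008, so this is not a small-sample effect.

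**Wider range:** a separate exponential model (35% vaccinated, immunosuppression 25-50% v 10%, RRR 1.0 v 1.5) gave log biases of 0.057, 0.098 and 0.159, that is, ratios of 1.06 to 1.17. With RRR 2.0 the log bias was 0.271, a ratio of 1.31. Standard errors from n = 496 were about 0.20, rising 3-14% with the added interaction.

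**Direction:** the ratio exceeds 1, so the agent looks relatively better in the vaccinated, whereas Hypothesis 1 expects a ratio below 1. In the immunosuppression model the same formula has a negative sign: the immunosuppressed are more often vaccinated, and Hypothesis 1 gives the vaccinated less benefit. There the bias masks Hypothesis 2.

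**Vaccine type:** three codings for the unvaccinated were compared.
- Missing: complete-case fitting drops all of them.
- A third level for none, beside vaccination status: rank 5 with 6 columns.
- An mRNA indicator equal to 0 in the unvaccinated: full rank, 5 of 5.

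**The case against.** E-7 never says main effects only; that is inferred from its covariate wording together with section 9.1. The inference is sound, because section 9.1 names an interaction when it wants one.

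The cross-classified subgroups in E-7 would show the treatment effect by vaccination within levels of immunosuppression. A reader might infer that the two hypotheses cannot be separated at all; those subgroups show otherwise. They are exploratory and conditional on numbers, however, so they do not repair the main model.

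A reader might also infer that a pure immunosuppression effect would be reported as a vaccination effect. Only part of it crosses over: 0.057, 0.098 and 0.159 divided by ln 1.5 = 0.405 give 14%, 24% and 39% on the log scale.

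The bias is modest beside the noise. In the biased rows of the table it runs from 0.040/0.218 = 0.2 to 0.220/0.218 = 1.0 standard errors. With a log bias of 0.057 and a standard error of 0.20, root-mean-square error is √(0.057² + 0.20²) = 0.21 without the extra term and 0.20 × 1.03 = 0.21 with it. The SAP already warns that subgroup results have low power and no error control. That warning stands, but it concerns chance findings and not a systematic shift.

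Finally, the vaccine-type gap might be read as making the model unfittable, or as a reason to drop the covariate. Neither follows. Ordinary nested coding is estimable, nothing in the SAP prescribes complete-case deletion, and E-7 gives a reason for the covariate (immunity wanes differently between vaccines).

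**Conclusion.** The point holds as a limited defect in a secondary analysis. The E-7 adjustment, as naturally read, does not achieve its stated purpose: the treatment-by-vaccination interaction stays confounded if immunosuppression modifies the effect, and vice versa.

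Across the assumed range (immunosuppression 20-50% v 10%, effect ratio 1.5-2.0) the spurious ratio is about 1.04-1.31. At n = 485 false positives were about 5-10% in most assumed scenarios and 18% in the most extreme one tabulated. All of this rests on prevalences and effect ratios that the documents do not supply, on yes/no factors, and on time to sustained recovery only. If immunosuppression is not an effect modifier, there is no bias.

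A reader might infer that the bias would falsely support Hypothesis 1. Under the SAP's own hypotheses and correlation it works the other way. The primary analysis and the randomised comparisons within each subgroup are unaffected. The vaccine-type point is only a missing coding rule.

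**What to change.** Before unblinding, amend E-7 (or Appendix G for MP0420) so that each heterogeneity model contains both the treatment-by-vaccination and the treatment-by-immunosuppression interactions. Report each adjusted for the other, beside the planned estimates. Since each factor has three levels, this adds two terms to each model.

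Keep vaccine type. State that it is coded as an mRNA indicator nested within the vaccinated and set to 0 for the unvaccinated, so that no unvaccinated participant is dropped from either model.

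The cost is a few lines of SAP text and somewhat wider intervals for the interactions. The standard error rose by about 1-7% in the tabulated scenarios and by 3-14% in the wider range; 14% corresponds to about 30% more variance (1.14² = 1.30). Where the bias is smallest, the gain in accuracy is negligible, which is a reason to show both sets of estimates and not to replace one with the other.

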#### H5.1.1 *Potential benefits and risks from MP0420* Potential benefits

The potent antiviral activity of MP0420 has the potential to reduce the viral load of SARS-CoV-2, which could translate into beneficial clinical effects. This statement is supported by preclinical studies summarized below. MP0420 demonstrated high affinity binding to its target, the RBD in the spike protein of SARS-CoV-2, with no observed off-target binding as measured in Retrogenix assay and GLP TCR study [5]. MP0420 has been shown to potently neutralize SARS-CoV-2 in live virus assays. In addition, several known spike mutations did not affect the antiviral activity of MP0420 in neutralization assays using VSVG-pseudotypes [5, 6]. MP0420 was shown to neutralize variants of the UK originated lineage B.1.1.7 (del69-70, del145, N501Y, A570D, D614G, P681H, T716I, S982A, D1118H) and the South African originated lineage B.1.351 (D80A, D215G, E484K, N501Y, A701V) as efficiently as the wild-type Wuhan virus with IC50 values in the low single-digit ng/mL range. MP0420 also gave potent protection against individual mutations reported in currently circulating SARS-CoV-2 strains: N501Y, E484K, K417E, Y453F, D614G, S477N, A222V, G446V, G476S, T478I, P479S, V483A, Q493K and F490S.

Significant reduction in viral load and pathogenesis was observed in five studies conducted using two hamster models. MP0420 dose-dependently reduced virus titers in the lung, throat and nasal turbinates. Disease-related body weight loss was reduced and a protective effect on lung tissues was observed. Please refer to the IB for details [5].

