Between March 1 and September 30, 2021, 1455 participants were randomized to AZD7442 or placebo. The enrollment period included time periods both prior to and after the emergence of the Delta variant. Higher levels of plasma nucleocapsid antigen at baseline were observed during enrollments in July-September compared to enrollments in March-June, which coincided with the emergence and global replacement of the Alpha/other viral variants with the Delta variant. Observational studies suggest worse clinical outcome from being infected with the Delta than the Alpha viral variant.

Research Question 1: Does the treatment effect of AZD7442 versus placebo differ based on the viral strain that the participant is infected with?

Hypothesis: The benefit of AZD7442 differs between participants who were infected with the Delta variant versus those who were infected with other viral variants.

Justification: The AZD7442 nMAb combination binds to non-overlapping epitopes on the SARS-CoV-2 Spike protein, presumably decreasing viral replication and dissemination by blocking the ability of the Spike protein to bind to host cells expressing ACE2. As such, participants who were infected with the Delta variant versus those who were infected with other viral variants may benefit more from treatment with ADZ7442. This may be particularly pronounced in the subset of participants who have not yet mounted their own endogenous neutralizing antibody response.

An alternate hypothesis is that the dose of AZD7442 is better able to contain viral replication among persons infected with a less virulent viral strain, and hence the relative benefit from using AZD7442 could be more pronounced among participants infected with non-Delta than Delta viral variants.

Statistical analyses:

To address the hypothesis of a differential treatment effect, the investigational agent will be compared versus placebo in subgroups by SARS-CoV-2 variant (Delta versus other), and tests for differential treatment effects across the subgroups will be performed by testing for

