interactions between the treatment and subgroup indicators. Subgroup analyses will be performed for time to sustained recovery (primary efficacy outcome) and key safety outcomes, including the composite outcomes of *grade 3 or 4 AEs, SAEs, organ failure, serious infections, or death* through Day 28; *SAEs, organ failure, serious infections, or death* through Day 90. Statistical methods for the subgroup analyses are described in Section 9.1.

Because the composition of the study population may have changed over time, including an increase in the proportion of participants infected with the Delta variant, an increase in the proportion of vaccinated persons in the general population, and changes in the population with respect to supplementary oxygen requirements, models for these subgroup analyses will also consider adjustment for vaccination status, and for supplementary oxygen requirements at study entry (categories of the ordinal pulmonary outcome).

Research Question 2: What is the effect of specific mutations?

AZD7442 is a combination therapy targeting non-overlapping epitopes in the RBD. While mutations found in variants can impact the binding of either one of the nMAbs (including at positions R346, K444, V445, G446, N450, L452 G476, E484, Q493K) the combination is hypothesized to retain activity. Nevertheless, high quality sequencing of the Spike gene will provide information on any relevant RBD mutations that could impact binding of one or both nMAbs.

Hypothesis: The relative benefit of AZD7442 (vs placebo) is larger for those infected with virus without mutations at binding-relevant positions compared with those with such virus mutations.

Statistical Analyses:

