It is expected that the rate of viral variants than contains mutations at the binding-relevant positions is low, with correspondingly low power for statistical tests. For individual mutations that occur at sufficiently high rates, and pooled across mutations, subgroup analyses will be performed comparing AZD7442 versus placebo within subgroups by the presence versus absence of the mutations. The treatment effect will be compared across subgroups by testing for an interaction between the treatment and subgroup indicators. Subgroup analyses will be performed for time to sustained recovery and key safety outcomes, as described above; statistical methods are described in section 8.4 of this SAP. Models will include vaccination status and supplementary oxygen requirements (categories of the ordinal pulmonary outcome) at baseline as covariates.

These are exploratory analyses. In addition, if mutations on other sites occur with sufficient frequency, similar analyses will be performed to identify mutations that are associated with the outcome of the treatment.

E-9 Missing Outcomes and Missing Baseline nAb Status

Missing primary outcome results and 90-day survival status due to withdrawal of consent or loss to follow-up will be summarized by treatment group, and tests will be performed whether the proportion of missing data is independent of the treatment assignment. Baseline factors related to these missing outcome data, overall and for each treatment group, will be determined using logistic regression. Candidate baseline factors for this investigation include, but are not limited to, categories of oxygen requirement (pulmonary outcome), antigen levels, and the disease progression risk score (section 13.2). Summaries of missing outcome data will also include when patients with missing data were last seen and their last known clinical status (e.g., discharged, hospitalized, alive at home).

As sensitivity analyses, multiple imputation may be used to estimate missing outcomes. Other sensitivity analyses may also be considered following unblinding when the final extent of missing data is known and the pattern of missing data is investigated. As of December 28, 2021, 6 participants had withdrawn consent and 23 additional patients had unknown sustained recovery status at 90 days. Follow-up is ongoing, including attempts to reach patients who are lost to follow-up. Thus, these numbers are likely to change.

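### SAP E-8, Research Question 2: the mutation models carry no lineage term, so a common mutation that marks a lineage can be credited with that lineage's treatment effect (minor; exploratory analyses)

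*SAP*

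**What the plan says.** SAP E-8 has two parts. Research Question 1 compares Delta with other variants, under the hypothesis: "The benefit of AZD7442 differs between participants who were infected with the Delta variant versus those who were infected with other viral variants". The section records that recruitment straddled the change of variant: "The enrollment period included time periods both prior to and after the emergence of the Delta variant".

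The second part is headed "Research Question 2: What is the effect of specific mutations". It forms subgroups by presence or absence of mutations at nine positions considered relevant to binding, E484 among them, both for each sufficiently frequent mutation and pooled. The test is: "The treatment effect will be compared across subgroups by testing for an interaction between the treatment and subgroup indicators". The adjustment is: "Models will include vaccination status and supplementary oxygen requirements (categories of the ordinal pulmonary outcome) at baseline as covariates". The plan then extends to other sites: "similar analyses will be performed to identify mutations that are associated with the outcome of the treatment". E-8 expects mutations at the binding positions to be rare and labels the work exploratory.

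For methods, this part points to SAP section 8.4, but section 8 ends at 8.3. If section 9.1 is meant, its general rule adds only disease severity, and E-5 states that AZD7442 enrolled nobody in severity stratum 2.

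Appendix G carries the section over: "E-8 (viral strain) of Appendix E will be carried out for MP0420".

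**The concern.** Mutations occur in sets that define lineages. Protocol H5.1.1 gives an example, "the South African originated lineage B.1.351 (D80A, D215G, E484K, N501Y, A701V", which includes a change at E484, one of E-8's listed positions. A mutation frequent in one lineage and rare elsewhere therefore stands in for that lineage. If lineage modifies the treatment effect, as Research Question 1 supposes, the treatment-by-mutation test picks up that modification whether or not the mutation does anything.

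The error can run either way. Research Question 2 expects more benefit without the binding-site mutations. If the marked lineage benefits less, an inert marker would look like loss of binding. If it benefits more, a real loss of binding could be hidden. The scan of other sites is exposed in the same way.

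The plan accepts the principle elsewhere. E-7 adjusts the vaccination and immunosuppression subgroup models for each other because the two factors are correlated. Lineage, which Research Question 1 already needs, gets no such treatment here.

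**Working it through.** **Inputs from the SAP.** AZD7442 mITT 1,417 and 1,195 sustained recoveries (E-3); 1:1 allocation (section 1.3); two-sided 5% tests (section 3); MP0420 mITT 485 (Appendix G).

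**Assumptions, not in the documents.** 50% Delta; a Delta-versus-other ratio of recovery rate ratios (RRRs) of 1.2 to 1.32; the mutation prevalences below; no true mutation effect.

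**Step 1: the plan's own figure.** Detectable RRR = exp(2(z_0.975 + z_power)/√events). With 1,195 events this gives 1.206, 1.189 and 1.176 at 90%, 85% and 80% power, matching Table E-2. Research Question 2 has no power figure of its own.

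**Step 2: the inherited effect.** Let λ = P(Delta | mutation) − P(Delta | no mutation). With no mutation effect, the apparent interaction ratio is (lineage ratio)^λ, with SE = √(4/E1 + 4/E0), where E1 and E0 are events with and without the mutation (events taken as proportional to group size).

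Common marker (95% of Delta, 5% of other):
- λ = 0.95 − 0.05 = 0.90 and SE = √(4/597.5 + 4/597.5) = 0.116.
- Ratio 1.2: z = 0.90 × 0.182/0.116 = 1.42, rejection 29%.
- Ratio 1.32: z = 0.90 × 0.278/0.116 = 2.16, rejection 58%.

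Rare mutation (5% of one group, none in the other, so 2.5% overall):
- λ = 1 − 0.475/0.975 = 0.513 and SE = √(4/29.9 + 4/1165.1) = 0.371.
- z = 0.25 or 0.38, rejection 5.7% or 6.7%.

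| Mutation in Delta / other | Overall prevalence | Rejection, ratio 1.2 | Rejection, ratio 1.32 |
|---|---|---|---|
| 5% / 0% | 2.5% | 5.7% | 6.7% |
| 10% / 0% | 5% | 6.5% | 8.5% |
| 20% / 0% | 10% | 8.2% | 12.6% |
| 95% / 5% | 50% | 29% | 58% |

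With the two groups equal in size, the first three rows are the same for a mutation confined to the other group. Simulation in Cox form (1,200 runs per setting) gave 30% and 59% for the last row.

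**Step 3: what removes the bias.** Simulation with 1,000 runs per setting, a rate model, N = 1,417, 50% Delta, mutation in 90% of Delta and 5% of other:

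| Lineage RRRs | No lineage term | Lineage main effect only | Lineage and treatment × lineage |
|---|---|---|---|
| 1.25 vs 1.00 | 34% | 34% | 5% |
| 1.50 vs 1.00 | 83% | 84% | 5% |

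The main effect alone does nothing; the interaction term restores the nominal level. When the lineage RRRs are equal, rejection stays at about 4-6% in all three models.

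**Step 4: the price.** With φ the correlation between mutation and Delta, the variance of the interaction estimate grows by 1/(1 − φ²). At 90%/5%, φ² = 0.25 × 0.85²/(0.475 × 0.525) = 0.724, a factor of 3.6. At 98%/2% the factor is 12.8. A perfect marker cannot be separated at all.

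**Step 5: MP0420.** Assuming the same recovery proportion, 485 × 1,195/1,417 = 409 events. Rejection is 5.2-7.5% for one-lineage mutations at 2.5-10% prevalence. For the 95%/5% marker it is 13% at ratio 1.2 and 24% at 1.32; simulation of the latter gave 25%, and 6% with the lineage term.

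**The case against.** **Rarity.** E-8 itself expects mutations at the binding positions to be uncommon. In that setting the inflation is a few percentage points at most. This stands, and it limits the 30-60% figures to a listed position that proves common or to the scan of other sites. It does not remove the point, since individual tests are reserved for mutations that are frequent enough.

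**No documented Delta marker.** The documents do not list Delta's mutations. Their only link to a listed position is E484K in B.1.351, which falls in Research Question 1's comparison group. This also stands: a Delta-versus-other term would not separate E484K from the rest of B.1.351.

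**Over-adjustment.** Lineages are defined by their mutations. If a lineage's effect works through its binding-site changes, a treatment-by-lineage term absorbs part of what Research Question 2 seeks. That is a good reason to keep the planned model and set the second one beside it.

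**Exploratory status.** The analyses are labelled exploratory, and section 9.1 asks for caution about subgroup results. This lowers the severity. But the caution there names limited power and type I error. Confounding by lineage is a bias, and a larger sample makes it more significant.

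**Conclusion.** The omission is real and its consequence is conditional. If lineage modifies the treatment effect, the planned models can credit a lineage-marking mutation with an effect it does not have, or hide one it has. The inflation is slight for rare mutations (about 6-7% at 2.5% prevalence), modest at 10% (8-13%), and large only for common markers (about 30-60% at 95%/5%). All of this rests on an assumed Delta share, an assumed lineage ratio of 1.2 to 1.32 and no true mutation effect.

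Two stronger readings are tempting. A reader might infer that Research Question 2 cannot answer its question at all. The documents do not support that: mutations that vary within a lineage remain informative, and without a lineage difference the tests keep their level. A reader might also infer that a Delta effect will be reported as loss of binding. That needs Delta to benefit less, which E-8 gives only as its alternate hypothesis; its leading justification points the other way.

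No primary result, safety boundary or stopping decision uses these tests. Severity is minor.

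**What to change.** Add to E-8, Research Question 2:

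- For each mutation frequent enough to test, report beside the planned model a second one with lineage and treatment × lineage, or a within-lineage comparison. State that a lineage main effect alone is not enough.
- Define lineage by the one the mutation actually marks (for example B.1.351 for E484K), not only Delta versus other.
- Attribute an effect to a mutation only if it persists in the second model.
- Report mutations essentially fixed in a lineage as not separable from the lineage result, and show the pooled mutation analysis with and without them.
- Apply the same rule to MP0420 through Appendix G.
- Correct the pointer to section 8.4.

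This takes a few sentences and no new data, since sequencing already supplies lineage. The cost is precision (variance about 3.6-fold at 90%/5%) and no separate conclusion for lineage-fixed mutations. Where a lineage is too sparse for the second model, the report should say so.
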